6.1.1 Lost to Follow Up

Every reasonable effort is to be made to contact any subject lost to follow-up during the course of the study to complete study-related assessments, record outstanding data, and retrieve study drug.

6.2 Discontinuation of the Site

If an investigator intends to discontinue participation in the study, the investigator must immediately inform the sponsor.

6.3 Discontinuation of the Study

The sponsor may terminate this study or treatment arm, prematurely, either in its entirety or at any study site, for reasonable cause provided that written notice is submitted in advance of the intended termination. Advance notice is not required if the study is stopped due to safety concerns. If the sponsor terminates the study for safety reasons, the sponsor will immediately notify the investigator and subsequently provide written instructions for study termination.

7 STATISTICAL METHODOLOGY

A Statistical Analysis Plan (SAP) will be written to provide details of the analysis, along with specifications for tables, listings and figures to be produced. The SAP will be finalized before the database hard lock. Changes from the analyses planned in SAP that affect the statistical analysis will be documented in the Clinical Study Report (CSR).

In general, continuous data will be summarized with descriptive statistics (number of subjects, mean, SD, minimum, median and maximum), and frequency and percentage for categorical data.

7.1 Sample Size

The primary objective of this study is to assess long-term safety and tolerability. The sample size in this study is not calculated based on the statistical power for efficacy evaluation to detect treatment difference.

The total sample size will be 1740, which will be randomly assigned 1:1:1 to a fezolinetant 45 mg once daily group (580), fezolinetant 30 mg once daily group or placebo group (580). This sample size would provide high probability to observe events of special interest that has with a fairly low background event rate that is less than 1%. With the sample size, the following table illustrates the probability of observing 1 or more events, 2 or more events and 3 or more events for different background event rate.

	Fezolinetant 45 mg once daily/Fezolinetant 30 mg once daily/Placebo		
Sample Size (1:1:1)	n = 580		
Background Event Rate	Prob(#>=3)	Prob(#>=2)	Prob(#>=1)
0.10%	2.11%	11.53%	44.03%
0.20%	11.18%	32.29%	68.69%
0.30%	25.33%	51.94%	82.49%
0.40%	40.94%	67.43%	90.22%
0.50%	55.46%	78.62%	94.54%
0.60%	67.63%	86.28%	96.95%
0.70%	77.16%	91.35%	98.30%
0.80%	84.27%	94.62%	99.05%
0.90%	89.38%	96.69%	99.47%

Prob(#>=1) means the probability of observing 1 or more events.

Prob(#>=2) means the probability of observing 2 or more events.

Prob(#>=3) means the probability of observing 3 or more events.

In addition, if an assumed background rate of 0.26% such as for endometrial hyperplasia, this sample size would provide the final number of evaluable subjects to demonstrate that the point estimate is less than or equal to 1% and upper bound of 1-sided 95% CI to be $\leq 4\%$ with at least 95% probability assuming up to 60% (including baseline, ED and subject refusal of endometrial biopsy at EOT) of subjects may not have evaluable biopsy data.

7.2 Analysis Sets

7.2.1 Full Analysis Set (FAS)

The full analysis set (FAS) will consist of all subjects who are randomized and receive at least 1 dose of study drug. This will be the primary analysis set for efficacy analyses. The randomized treatment for each subject will be used for summaries by treatment group based on the FAS, even if a subject erroneously received a different treatment.

7.2.2 Safety Analysis Set (SAF)

The safety analysis set (SAF) consists of all randomized subjects who took at least 1 dose of study drug, and will be used for safety analyses. A subject erroneously receiving a treatment different from their randomized treatment will be assigned to the treatment group that the patient received as first dose.

7.2.3 Pharmacokinetic Analysis Set (PKAS)

The pharmacokinetic analysis set (PKAS) consists of the administered population for which sufficient plasma concentration data is available to facilitate derivation of at least 1 pharmacokinetic parameter and for whom the time of dosing on the day of sampling is known. Additional subjects may be excluded from the PKAS at the discretion of the pharmacokineticist. Any formal definitions for exclusion of subjects or time-points from the

PKAS will be documented in the in the Classification Specifications and determined the Classification Meeting.

7.2.4 Pharmacodynamic Analysis Set (PDAS)

The pharmacodynamic analysis set (PDAS) will include the subjects from the administered population for whom sufficient pharmacodynamic measurements were collected. The PDAS will be used for all analyses of pharmacodynamic data.

7.3 Demographics and Baseline Characteristics

The demographic summary will include age, sex, race, ethnicity, smoking status and prior HT use. Baseline characteristics include caffeine used, weight, body mass index, diagnosis of the target disease, severity and duration of disease. Demographics and baseline characteristics will be summarized by treatment group as well as for all treatment groups combined.

7.3.1 Subject Disposition

The number of subjects who are screened, randomized and treated will be summarized. The number and percentage of subjects who completed and discontinued treatment and reasons for treatment discontinuation will be presented for all randomized subjects and subjects in the SAF by treatment group and overall. All disposition details and dates of first and last evaluations for each subject will be listed.

7.3.2 Previous and Concomitant Medications

All previous and concomitant medications will be summarized.

7.3.3 Medical History

Medical history for each subject will be presented in a listing.

7.4 Analysis of Efficacy

No efficacy data will be collected for this study.

7.5 Analysis of Exploratory Endpoints

The exploratory endpoints include the MENQOL and the EQ-5D-5L which will be assessed at baseline and weeks 4, 12, 24 and 52. The exploratory endpoints will be analyzed for the FAS set. Summary statistics will be provided by treatment group.

The exploratory variables include the effect of fezolinetant on the following:

- Mean change on the MENQOL Total Score from baseline to specified time points.
- Mean change on the MENQOL Domain Scores from baseline to specified time points.
- Mean change on the EQ-5D-5L Total Score from baseline to specified time points.
- Change from baseline to specified time points in serum concentrations of sex hormones and SHBG [see Section 7.2.4 Pharmacodynamic Analysis Set (PDAS)].
- Plasma concentrations of fezolinetant and the fezolinetant metabolite ESN259564 at specified time points [see [Section 7.2.3 Pharmacokinetic Analysis Set \(PKAS\)](#)].

For the treatment comparison of continuous endpoints, a mixed model for repeated measures (MMRM) will be used. The model will include treatment, visit, and smoking status (current vs former/never) as factors, with baseline weight and baseline measurement as covariates, as well as an interaction of treatment by visit and an interaction of baseline measurement by visit., with an unstructured variance-covariance.

7.6 Analysis of Safety

Overall long-term safety of fezolinetant will be the primary objective of this study. The safety assessments include adverse events, laboratory assessments, vital signs, C-SSRS, Pap test, physical examination, ECG, endometrial health assessment and imaging (mammogram, DXA, TVU). Safety analysis will be conducted on the SAF.

Primary Safety Variables:

The primary variable will require the evaluation of the safety of fezolinetant on the following:

- Frequency and severity of AEs
- Percentage of subjects with endometrial hyperplasia
- Percentage of subjects with endometrial cancer

Secondary Safety Variables:

- Change from baseline in endometrial thickness at 12 months
- Percentage of subjects with disordered proliferative endometrium
- Change from baseline in BMD and TBS at hip and spine at 12 months
- Vital signs: sitting systolic and diastolic blood pressure and pulse rate
- Laboratory tests: hematology, biochemistry and urinalysis
- C-SSRS
- ECG parameters

For each AE of special interests a summary statistics will be provided and the rate, odds ratio, and their corresponding 2-sided 95% confidence intervals will be presented. For the treatment comparison of bone density and endometrial thickness, an analysis of covariance model will be used. The model will include treatment and smoking status (current vs former/never) as factors, with baseline weight and baseline as covariates.

7.6.1 Adverse Events

A TEAE is defined as an AE observed after starting administration of the study drug and 21 days after the last dose of study drug.

The number and percentage of subjects with treatment-emergent AEs, SAEs, AEs leading to withdrawal of treatment and AEs related to study drug will be summarized by SOC, preferred term and treatment group. The number and percentage of AEs by severity will also be summarized. All AEs will be listed.

A study drug-related TEAE is defined as any TEAE with a causal relationship of YES by the investigator.

AEs will be coded using MedDRA. An AE with onset at any time from first dosing until last scheduled procedure will be classified as treatment-emergent for inclusion in the summary tabulations.

An overview and separate summaries by SOC and preferred term of the number and percentage of subjects with TEAEs, drug-related TEAEs, TEAEs leading to withdrawal of treatment and TEAEs excluding SAEs and drug-related TEAEs leading to withdrawal of treatment will be presented by treatment group. Also included in the overview are the number and percentage of subjects with serious TEAEs, drug-related serious TEAEs, TEAEs leading to death, and drug-related TEAEs leading to death.

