5.8 Adverse Events and Other Safety Aspects

5.8.1 Definition of Adverse Events

An AE is any untoward medical occurrence in a subject administered a study drug, and which does not necessarily have to have a causal relationship with this treatment. An AE can therefore be any unfavorable and unintended sign (including an abnormal laboratory finding), symptom, or disease (new or exacerbated) temporally associated with the use of a medicinal product whether or not considered related to the medicinal product.

In order to identify any events that may be associated with study procedures and could lead to a change in the conduct of the study, Astellas collects AEs even if the subject has not received study drug treatment. AE collection begins after the signing of the informed consent and will be collected until 21 days after the last dose of study drug or the subject is determined to be a screen failure.

Care will be taken not to introduce bias when detecting AEs and/or SAEs. Open-ended and non-leading verbal questioning of the subject is the preferred method to inquire about AE occurrences.

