5.8.6 Follow-up of Adverse Events

All AEs occurring during or after the subject has discontinued the study are to be followed up until resolved or judged to be no longer clinically significant, or until they become chronic to the extent that they can be fully characterized by the investigator.

If after the protocol defined AE collection period [see [Section 5.8.1 Definition of Adverse Event](#)], an AE progresses to a SAE, or the investigator learns of any (S)AE including death, where he/she considers there is reasonable possibility it is related to the study drug treatment or study participation, the investigator must promptly notify the sponsor.

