6.5.1 Adverse Events

Per protocol, a treatment emergent adverse event (TEAE) is defined as the AEs that occurred on or after first dose of study drug and 21 days after the last dose of study drug (when AE collection closes).

A study drug-related TEAE is defined as any TEAE with a causal relationship of YES by the investigator.

The sponsor has a list of events that they classify as "always serious" events. If an AE is reported that is considered by the sponsor to be an SAE per this classification as "always serious", the AE will be treated as an SAE in tables and listings, and flagged as 'always serious' in AE listings.

An overview table will include the following

- Number of TEAEs,
- Number and percentage of subjects with TEAEs,
- Number of drug related TEAEs,
- Number and percentage of subjects with causally drug related TEAEs,
- Number of serious TEAEs,

- Number and percentage of subjects with serious TEAEs,
- Number of serious drug related TEAEs,
- Number and percentage of subjects with serious drug related TEAEs,
- Number of TEAEs leading to permanent discontinuation of study drug,
- Number and percentage of subjects with TEAEs leading to permanent discontinuation of study drug, and
- Number of deaths.

In order to adjust for differences in subjects' durations and the potential differential dropout rates between the treatment groups, an overview table to report exposure adjusted incidence rate (per 100 subject-years) for the above AE categories will be summarized. The total subject-years of exposure is calculated as the sum over subjects of the total duration of exposure divided by 365.25:

$$\sum_{i} \frac{ld_i - fd_i + 1}{365.25},$$

where fd_i and ld_i denote the first dose date of study drug and the last dose date of study drug for subject *i*.

The number and percentage of subjects with TEAEs in the following AE categories will be summarized for each treatment group by system organ class (SOC), high level term (HLT) and preferred term (PT):

- TEAEs
- drug related TEAEs.

The number and percentage of subjects with TEAEs in the following AE categories will be summarized by SOC and PT:

- serious TEAEs,
- drug related serious TEAEs,
- TEAEs leading to permanent discontinuation of study drug,
- drug related TEAEs leading to permanent discontinuation of study drug,
- TEAEs that equal to or exceed a threshold of 5.0% in any treatment group (threshold is based on PT).

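### The treatment-emergent definition goes by onset and has no worsening clause, so a screening AE that worsens on treatment is missed unless the site opens a new record

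*Protocol*

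**What the plan says.** Three sentences define a treatment-emergent AE (TEAE).

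- Protocol 7.6.1, first sentence: "A TEAE is defined as an AE observed after starting administration of the study drug", continuing to 21 days after the last dose.
- Protocol 7.6.1, later, for the summary tabulations: "An AE with onset at any time from first dosing until last scheduled procedure will be classified as treatment-emergent".
- SAP 6.5.1: "AEs that occurred on or after first dose of study drug and 21 days after the last dose of study drug".

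On collection, Protocol 5.8.1 states that "AE collection begins after the signing of the informed consent". Screening lasts up to 35 days, or 50 with a repeat biopsy (Protocol 2.2.1).

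Status is decided from dates. Protocol 7.11 uses imputed dates to settle whether an AE is treatment-emergent. Under SAP 6.10.2, an onset known only to a month and year before that of first dose stays before first dose.

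The first primary endpoint is "Frequency and severity of AEs" (Protocol 7.6). In SAP 6.5.1 the incidence, severity, seriousness and discontinuation tables are built from TEAEs, and events of special interest are defined within TEAEs.

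**The concern.** A long-term safety trial should capture two kinds of adverse effect: new events, and aggravation of events already present. The TEAE rule handles the first. It handles the second only if the aggravation arrives in the database as a separate AE with its own date, and neither document requires that for an AE that is already open.

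Two things are at stake. One is comparability across sites: the same clinical course could be counted at one site and not at another, depending on how staff use the AE form. The other is direction. If fezolinetant aggravates symptoms that began in screening, the omitted events fall more on the active arms, and the comparison with placebo is pulled toward no difference. If the drug has no such effect, randomisation should spread the omissions evenly and the comparison is little affected.

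**Working it through.** **Step 1: follow one case through the rules.** A woman has a mild AE that starts between consent and first dose. It is open at first dose and becomes severe or serious during treatment.

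| How the site records it | Onset date | TEAE under the onset sentence (7.6.1) | Where it appears |
|---|---|---|---|
| Same record, severity or seriousness updated | Before first dose | No | Listings only |
| New record dated at the worsening | After first dose | Yes | TEAE, severity, seriousness and, if relevant, special-interest tables |

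The first sentence of 7.6.1 speaks of an AE being observed rather than of its onset. Read literally, it could admit any AE still open at first dose, worsened or not. SAP 6.5.1 speaks of AEs that occurred on or after first dose. A programmer does not get one rule from the three sentences, but the onset sentence is the one tied to the tables, and none of the three mentions worsening.

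**Step 2: look for a rule elsewhere that rescues the first row.**

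- The worst-severity rule in SAP 6.5.1 works among a subject's TEAEs. It cannot bring in a record that is not a TEAE.
- Protocol 5.2.2 makes a change in medical status after consent reportable as an AE or SAE. Protocol 5.8.1 includes exacerbated disease in the AE definition, and 5.8.1.1 covers clinically significant test results that worsen from baseline. These say what must be reported. They do not say whether an open AE gets a new record and onset date.
- SAP 6.10.2 imputes a wholly missing onset to the first dose date, which makes that AE treatment-emergent. It does nothing for an AE with a known pre-dose onset.

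No rule in either document moves the case from the first row to the second.

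**Step 3: size.** The documents give no rate for AEs open at first dose or for their worsening, so the loss cannot be estimated. The plan's own detection table gives a scale.

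Inputs: n = 580 per arm and background rate p (Protocol 7.1, SAP 3). Formula: P(X ≥ r) with X ~ Binomial(580, p). At p = 0.50%, P(X ≥ 1) = 1 − 0.995^580 = 94.54% and P(X ≥ 3) = 55.46%, as the plan states. All 27 cells reproduce; the largest difference is 0.004 percentage points.

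Now suppose that a share f of the relevant events began in screening and goes uncounted, and replace p by p(1 − f). The values of f are assumptions for illustration only.

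| f | Counted rate | P(≥ 1 event) | P(≥ 3 events) |
|---|---|---|---|
| 0 | 0.500% | 94.54% | 55.46% |
| 5% | 0.475% | 93.68% | 52.02% |
| 10% | 0.450% | 92.69% | 48.44% |
| 20% | 0.400% | 90.22% | 40.94% |

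The last row matches the plan's own row for 0.40%. For a rare special-interest event, the screening AE would itself have to be of that rare type, so f is likely to be small there. One woman is 1/580 = 0.17 percentage points of an arm.

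**The case against.** The strongest reply is that the protocol already makes worsening reportable. A screening event that becomes severe after dosing is a change in medical status since consent (5.2.2), and the AE definition includes exacerbation (5.8.1). If sites report the worsening with its own date, it is a TEAE and nothing is lost. The eCRF instructions, which Protocol 12.2.3 says describe form completion and which are not among these documents, may already require a new record. This stands to the extent that the loss is conditional. It does not close the gap, because the protocol and SAP leave the outcome to site practice.

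Three stronger readings are tempting, and the documents do not support them.

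- A reader might infer that these events are always omitted, or lost altogether. They are counted if re-recorded. Protocol 7.6.1 lists all AEs, and the SAP overview counts deaths without a TEAE restriction. Listings do not, however, give a comparison between arms.
- A reader might take "an AE progresses to a SAE" in Protocol 5.8.6 as a rule that a worsening AE stays one record. That sentence concerns notifying the sponsor after the AE collection period. It sets no rule for AEs open at first dose.
- A reader might cite liver tests mildly raised at screening. On-treatment ALT, AST, ALP and bilirubin thresholds are tabulated from laboratory values (Protocol 7.6.2, SAP 6.5.2.1), and shifts from baseline are shown (SAP 6.5.2), whatever the AE onset date.

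The affected group is also narrow. Conditions present before consent are medical history, and their exacerbation on treatment is a new AE. A woman with any other TEAE still counts as a subject with a TEAE.

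**Conclusion.** The point holds in a limited form. Both documents set treatment-emergence by timing and contain no worsening clause, and in the SAP the tables for the first primary endpoint rest on that status. An AE that begins between consent and first dose, remains open and worsens on treatment is left out of those tables unless the site opens a new record.

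The effect is probably small, and the documents do not allow it to be estimated; the detection figures above only illustrate what an assumed share would do. A bias toward no difference from placebo depends on the drug aggravating existing symptoms, which the documents neither show nor rule out. Because this trial's purpose is to detect harm, that is the unfavourable direction, and the gap is cheap to close.

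**What to change.** In Protocol 7.6.1 and SAP 6.5.1, use one definition: a TEAE is an AE with onset on or after first dose, or an AE with onset before first dose that increases in severity or becomes serious on or after first dose, within the same end window. Protocol 7.6.1 gives two ends for that window, 21 days after the last dose and the last scheduled procedure; settle on one in the same edit.

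Implement the clause by one method only. Instruct sites, in Protocol 5.8.1 and the eCRF guidelines, to enter the worsening as a new AE record dated at the worsening. The earlier record stays non-treatment-emergent. Reclassifying the earlier record as well would count the event twice in the number of TEAEs. A severity change overwritten on a single record would also be hard to place after first dose, because the documents do not show that severity changes are dated.

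The cost is one clause in each document, one line in the eCRF guidelines, and slightly higher AE percentages in all arms. If the eCRF instructions already require a new record, the protocol and SAP need only say so.

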7.6.2 Laboratory Assessments

For quantitative laboratory measurements descriptive statistics will be used to summarize results and change from baseline for subjects in the SAF by treatment group and time point.

Shifts relative to normal ranges from baseline to each time point during treatment period in lab tests will also be tabulated. Laboratory data will be displayed in listings.

Number and percentage of subjects with platelets $< 150 \times 10^9/L$ will be separately summarized for each treatment group. The liver safety assessments will be summarized by the categories below based on the measurements from ALP, ALT, TBL, AST and their combination. These parameters will be based on measurements from a central laboratory.

The subject's highest value during the treatment period will be used.

- $ALT > 3 \times ULN, > 5 \times ULN, > 10 \times ULN, > 20 \times ULN$
- $AST > 3 \times ULN, > 5 \times ULN, > 10 \times ULN, > 20 \times ULN$
- $ALT \text{ or } AST > 3 \times ULN, > 5 \times ULN, > 10 \times ULN, > 20 \times ULN$
- $ALP > 1.5 \times ULN$
- $TBL > 2 \times ULN$
- $(ALT \text{ or } AST > 3 \times ULN) \text{ and } TBL > 2 \times ULN$
- $(ALT \text{ or } AST > 3 \times ULN) \text{ and } ALP < 2 \times ULN \text{ and } TBL > 2 \times ULN$

The last 2 criteria where 2 or more parameters are evaluated will be with the measurements on the same day or up to 1 day apart.

